1.0 SYNOPSIS

Protocol Title: A Phase Ib/II, single center, placebo-controlled, randomized study in adult patients (≥ 18 years) with COVID-19 Respiratory Disease, to evaluate, Safety, Tolerability and mechanistic effect of Alvelestat on top of standard of care (COSTA).

Rationale: Neutrophils and neutrophil extracellular traps (NETs) have recently been established as a central feature of SARS-CoV-2 pathogenesis, and NET formation (NETosis) are associated with poor outcomes in patients hospitalized with COVID-19 (Zuo et al 2020; Barnes et al 2020). NETs are networks of extracellular DNA fibers, histones, myeloperoxidase (MPO) and neutrophil elastase (NE), released from neutrophils and involved physiologically in capturing bacteria. However, if uncontrolled, NETs are cytotoxic to endothelial and epithelial cells, acting as Damage Associated Molecular Pattern Molecules (DAMPs) and promoting cytokine release and thromboses (Kim et al 2019). Levels of NETs correlate with disease severity in ALI/ARDS (Li et al 2018) Neutrophil elastase is essential to NET formation (Papayannopoulos et al 2010) and remains active when decorating the NET fibers. The physiological inhibitor of NE is Alpha-1 antitrypsin (AAT), but studies in COVID-19 have shown this to be overwhelmed (McElvaney et al 2020). Providing NE inhibition therefore has potential to reduce both NET formation and damaging activity of existing NETs. In experimental models of ARDS, alvelestat, the NE inhibitor proposed for this clinical trial, protected the lung from inflammation and injury through NET inhibition (Li et al 2018). There is also evidence from clinical efficacy studies using NE inhibitors in ALI/ARDS. Sivelestat ('Elastpol') is a selective human neutrophil elastase inhibitor that is approved in Japan and South Korea for the treatment of ALI/ARDS accompanied by Systemic Inflammatory Response Syndrome. A meta-analysis of 6 randomised controlled trials in patients with all forms of ALI/ARDS, did not demonstrate an effect on mortality, Intensive Care Unit (ICU) or ventilator days. However, a sensitivity analysis detected a significant improvement in oxygen deficit measured by $\text{PaO}_2/\text{FiO}_2$ (SMD: 0.87; 95% CI: 0.39 to 1.35; $P < 0.001$, (Pu et al 2017) and oxygenation of Day 3 (Iwata et al 2010). Sivelestat appeared to have an effect on mortality in ARDS associated with disseminated intravascular coagulation (DIC) (Miyoshi et al 2014), a neutrophil-predominant disease, which is more closely aligned with COVID, and provides support for the NE mechanism.

Alvelestat (MPH966, AZD9668) is an oral, specific, potent human NE inhibitor (Stevens et al 2011). Alvelestat effectively inhibits neutrophil elastase activity in man, including during maximal neutrophil stimulation. It shows predictable systemic pharmacokinetic (PK) profile and therapeutically relevant concentrations in sputum (Gunawardena et al 2013). Clinical safety and efficacy experience has been gained in over 1000 healthy volunteers and patients with lung disease, including Chronic Obstructive Pulmonary Disease (COPD), cystic fibrosis and bronchiectasis (Kuna et al 2012; Elborn et al 2012; Stockley et al 2013). There has been evidence of mechanistic effect in clinical studies of neutrophil-driven diseases, with significant decrease in biomarkers of elastase activity in cystic fibrosis (Elborn et al 2012), and clinically significant improvement in lung function (Forced Expiratory Volume in 1 second [FEV1]) in bronchiectasis (Stockley et al 2013), with reduction in the pro-inflammatory biomarkers

Interleukin (IL)-6 and RANTES in sputum and blood observed in both these studies. Alvelestat is currently being investigated in ongoing clinical trials in alpha-1 antitrypsin deficiency lung disease (Clinical Trials.Gov NCT03636347; NCT03679598) and Bronchiolitis Obliterans Syndrome associated with chronic graft versus host disease (NCT02669251).

The scientific rationale for NE inhibition in SARS-CoV-2 infection, the evidence for an effect in other inflammatory lung diseases and the safety profile for alvelestat, supports investigating alvelestat in COVID-19. Here, we propose a pilot randomized, placebo-controlled trial assessing the safety and tolerability and exploring mechanistic effect on NETosis and clinical outcomes of alvelestat given on top of standard of care, compared to standard of care alone in patients hospitalized with COVID-19.

Overall Purpose and Design:

The purpose of this study is to evaluate the safety, tolerability, PK and explore mechanism of action and clinical effect of alvelestat in patients hospitalized with proven COVID-19 lung disease.

This is a Phase Ib/II single-center, 2:1 randomized, blinded, placebo-controlled, parallel group, first in disease study. The objectives are to determine the safety, tolerability and PK and to explore the mechanistic and clinical effect of the NE inhibitor alvelestat, 240mg orally twice per day for 5 or 10 days added to standard of care (SoC) versus placebo added to SoC, in adult patients (≥ 18 years) with COVID-19 respiratory disease.

Objectives and Endpoints:

Objective	Endpoint
Primary	
• To evaluate the safety and tolerability of alvelestat administered twice daily (bid) for 5 or 10 days	
By treatment group (alvelestat/placebo):
 
 • Numbers and % of subjects who experience at least 1 treatment-emergent adverse event to Day 60 (Safety Outcome Assessment) • Adverse events of special interest (liver function abnormalities, corrected QT interval, infections, and neutropenia) and clinically significant safety monitoring labs tests to EoT • Number and % of subjects that discontinue alvelestat to Day 5 or 10 • Number and % of subjects requiring dose reduction to Day 5 or 10 • Number and % of subjects with AE of headache on prospective questioning and CTCAE severity Grade to Day 5 or 10 • Change in vital signs, EKG, safety laboratory measures to Day 5 or 10 or EOT
Secondary	
• To evaluate the effect of alvelestat on blood pharmacodynamic markers of Neutrophil Extracellular Trap (NET) activation, elastase, inflammatory and coagulopathy activity	
By treatment group (alvelestat/placebo), change from baseline to Day 5 or 10 in:
 
 • Blood biomarkers of NETosis (cell-free DNA; citrullinated histone H3; Myeloperoxidase (MPO)-DNA complexes) • Blood biomarkers of inflammation (absolute neutrophil count; absolute lymphocyte count; neutrophil-lymphocyte ratio [NLR], C-Reactive protein, procalcitonin) • Pro-inflammatory cytokines IL-1beta, IL-6, IL-8, TNF-alpha) • Coagulopathy as measured by D-Dimer • Plasma desmosine/isodesmosine
• To explore the effect of alvelestat on pulmonary function	
By treatment group (alvelestat/placebo):
 
 • Change from baseline to Day 5 or 10 or EoT in SaO₂/FiO₂
• The effect of alvelestat on disease progression	
By treatment group (alvelestat/placebo):
 
 • Proportion of subjects alive and free of respiratory failure (without need for non-invasive or invasive mechanical ventilation, high flow oxygen, or Extracorporeal Membrane Oxygenation (ECMO) at Day 29

Objective	Endpoint

 The effect of alvelestat on clinical outcomes 	By treatment group (alvelestat/placebo): 
 Mortality rate at Day 90 safety endpoint Proportion of subjects alive and free of respiratory failure (without need for non-invasive or invasive mechanical ventilation, high flow oxygen, or ECMO) at Days 5, 10 and 60 Length of hospital stay Length of ICU stay Time to room air (those on supplemental oxygen at Baseline)

 The effect of alvelestat on disease severity 	By treatment group (alvelestat/placebo): 
 Percentage of patients deteriorating (>1 and >2 increase in WHO 9-point ordinal scale*) at Day 5, Day 10, Day 29 and Day 60 Percentage of patients improving (>1 and > 2 decrease in WHO 9-point ordinal scale) at Day 5, Day 10, Day 29 and Day 60

 To explore Pharmacokinetics (PK) in patients with COVID-19 	
 Plasma PK (sparse sampling taken pre or 1-2 hours post study drug dosing) in participants randomized to alvelestat.

* WHO 9-point ordinal scale:

0. Uninfected, no clinical or virological evidence of infection
1. Ambulatory, no limitation of activities
2. Ambulatory, limitation of activities
3. Hospitalized – mild disease, no oxygen therapy
4. Hospitalized – mild disease, oxygen by mask or nasal prongs
5. Hospitalized – severe disease, noninvasive ventilation or high flow oxygen
6. Hospitalized – severe disease, intubation and mechanical ventilation
7. Hospitalized – severe disease, ventilation and additional organ support – vasopressors, renal replacement therapy, extracorporeal membrane oxygenation
8. Death

2.0 SCHEDULE OF ASSESSMENTS (SOA)

a) For subjects completing treatment at Day 5

Study period	Screening Period	Study Treatment Period (once daily assessment for safety, respiratory support requirement ⁷ , level of hospital care [ward/ICU] and adverse events during hospitalization) ²					Safety and Efficacy Follow Up Period ²		
Visit Name	Screening	Baseline/ Randomize			End of Treatment (EoT) ⁸	Safety Follow Up (FU)	Clinical Outcome Assessment (COA)	Final Safety Follow Up (FU) 2	Mortality Follow Up
Study Day	Day-2 to Day -1 (screening and randomization can be on same day)	Day 1	Day 2	Days 3 and 4	Day 5	Day 10 (+/- 2 days)	Day 29 (+/- 2 days)	Day 60 (+/- 4 days)	Day 90 (+/- 7 days)
Eligibility check	X								
Informed consent	X								
Medical History	X								
Randomization		X							
Physical exam (full at screening, limited thereafter)	X	X	X	X	X	X			
Study Drug dosing		X	X	X	X				
Interim history, concomitant med, and adverse event recording ^{1, 2}	X	X	X	X	X	X	X ⁵	X ⁵	
Prospective headache query		X			X				
Pregnancy test (high sensitivity serum at screening, urine thereafter) ⁹	X					X			
Blood draw (screening and in-study safety monitoring) ^{2, 9}	X	X			X	X			

Visit Name	Screening	Baseline/ Randomize			End of Treatment (EoT)	Safety Follow Up (FU)	Clinical Outcome Assessment (COA)	Final Safety Follow Up (FU) 2	Mortality Follow Up
Study Day	Day-2 to Day -1 (screening and randomization can be on same day)	Day 1	Day 2	Days 3 and 4	Day 5	Day 10 (+/- 2 days)	Day 29 (+/- 2 days)	Day 60 (+/- 4 days)	Day 90 (+/- 7 days)
Blood draw (biomarkers)		X			X				
SaO ₂ /FiO ₂		X	X	X	X				
Blood (PK) ³		X			X ⁶				
EKG ^{2,4}	X	X			X ⁶				
Progression Endpoint (alive and free of respiratory failure, respiratory support level ⁷)					X	X		X ⁵	
Clinical outcomes assessments including WHO ordinal scale assessment		X	X	X	X	X	X	X ⁵	X ^{5,10}

¹ Only SAEs to be collected prior to randomization

² Investigations and examination performed as part of routine clinical assessment of COVID-19 may be used for eligibility and in study safety, adverse event and respiratory support requirement assessment

³ Time of PK and last dose of study medication prior to PK to be recorded in CRF

⁴ EKG to be taken 1-2 hours after study drug dosing when feasible

⁵ Telehealth visit if hospital discharge occurs before scheduled visit

⁶ PK and EKG can be taken on any one of Days 3-5

⁷ Level of respiratory support determined by need for room air, supplemental oxygen, high flow oxygen, non-invasive ventilation, intubation, mechanical ventilation or ECMO

⁸ Subjects who terminate study Before Day 5 should have EOT assessment and Safety Follow Up assessment 5 days +/- 2 days after last dose of study drug

⁹ If Screening and baseline are within 24 hours the tests do not need to be repeated at Baseline

¹⁰ Clinical outcome assessment of mortality only

b) For subjects extending study drug to Day 10

Study period	Treatment Period			Safety and Efficacy Follow Up Period ²		
	Visit Name	Extension Period	End of Treatment (EoT)	Safety Follow Up	Clinical Outcome Assessment (COA)	Final Safety Follow Up (FU) ⁴
Study Day		Days 6 to 9	Day 10	Day 15 +/- 2 days	Day 29 (+/- 2 days)	Day 60 (+/- 4 days)
Limited Physical exam		X	X	X		
Study Drug dosing		X	X			
Interim history, concomitant med, and adverse event recording ^{1,2}		X	X	X	X ⁵	X ⁵
Prospective headache query			X			
Pregnancy test (urine)				X		
Blood draw (in-study safety monitoring) ²		X	X	X		
Blood draw (biomarkers)			X			
SaO ₂ /FiO ₂		X	X	X		
EKG ^{2,4}			X	X ⁶		
Progression Endpoint (alive and free of respiratory failure, respiratory support level ⁷)			X			X ⁵
Clinical outcomes assessments including WHO ordinal scale assessment		X	X	X	X ⁵	X ⁵ X ^{5,8}

¹ Only SAEs to be collected prior to randomization² Investigations and examination performed as part of routine clinical assessment of COVID-19 may be used for eligibility and in study safety, adverse event and respiratory support requirement assessment³ Time of PK and last dose of study medication prior to PK to be recorded in CRF⁴ EKG to be taken 1-2 hours after study drug dosing when feasible⁵ Telehealth visit if hospital discharge occurs before scheduled visit⁶ PK and EKG can be taken on any one of Days 3-5⁷ Level of respiratory support determined by need for room air, supplemental oxygen, high flow oxygen, non-invasive ventilation, intubation, mechanical ventilation or ECMO⁸ Clinical outcome assessment of mortality only

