In the Phase 2b COPD program, there were 14 reported events of raised ALT or AST to $\geq 3 \times$ ULN across the studied doses (alvelestat) 5, 20, and 60 mg bid); there were no cases of Hy's law during the treatment period. Although definitive evidence of dose relationship was lacking, there was a suggestion of an increased incidence of liver transaminase elevations in patients on alvelestat for which there were no definitive alternative explanations. The highest transaminase elevations occurred in the highest alvelestat dose (60 mg bid). Elevations in hepatic biochemistry

assessments (transaminases) observed in patients in the alvelestat studies were confounded by alcohol or by concomitant medication, but an effect of alvelestat cannot be excluded at this time. COVID-19 disease is frequently associated with mild elevations in transaminases with increases >ULN of 75% and 2XULN in 45% of hospitalized patients (Phipps et al 2020). Elevation in alkaline phosphatase and total bilirubin are uncommon, and severe liver damage/failure has not been reported to date (Tian & Ye 2020). However, patients may be on multiple medications with the possibility of drug-related hepatotoxicity and greater sensitivity to any potential effects of alvelestat. As mild elevations of transaminases are common, in order to assess for any hepatic effects in the target population, participants with transaminases up to 3X ULN will be eligible, but only if there is no elevation of bilirubin due to liver dysfunction. In summary, exclusion criteria for clinically relevant hepatic disease, close observation and frequent in-study monitoring, and study treatment discontinuation criteria are in place to protect the safety of the subjects and liver abnormalities are included as adverse events of special interest (AESI).

There were no other clinically relevant changes in clinical chemistry data in the completed studies with alvelestat. There were also no clinically relevant changes in urinalysis were observed in the completed studies with alvelestat. There were no changes in EKG or vital signs data that indicated a clear treatment effect of alvelestat. However, in light of the minor changes in QTc in the dog toxicology, exclusion criteria and regular EKG monitoring at the time of peak concentrations of study treatment and discontinuation criteria will be applied in the study. Clinically significant changes in EKG are also included as an AESI.

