Defects in *ELANE*, the gene that encodes neutrophil elastase, are associated with neutropenia and susceptibility to infection. To date, no increases in rate or severity of infection or neutropenia have been reported with alvelestat. However, patients with COVID-19 are susceptible to sepsis and may be on immunosuppressive drugs, such as systemic corticosteroids that increase infection susceptibility. Patients with neutropenia will be excluded, new onset of neutropenia will constitute a patient stopping criterion, and infections will be an AESI to monitor the safety profile in this population.

The potential phototoxicity risk will be managed by subject guidance on reducing intense sun exposure through covering exposed skin and use of sun block as needed.

At present, based on the cumulative review of the data and with no new safety issues seen in the ongoing studies with dosing up to 240 mg bid of alvelestat, the benefit-risk balance supports the clinical development of alvelestat in COVID-19. The potential or theoretical safety concerns on liver function, QTc changes, and susceptibility to infection are manageable through exclusion criteria, monitoring, study treatment discontinuation criteria

More detailed information about the known and expected benefits and risks and reasonably expected AEs of alvelestat may be found in the current version of the alvelestat Investigator's Brochure.

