7.1 Treatments Administered

There are no bioavailability data to support administration of alvelestat given dissolved in fluid or as broken/crushed tablets for administration via nasogastric or other enteric feeding tube. If participants are unable to swallow tablets orally, study drug treatment needs to be discontinued (Section 8.1).

Study Treatment Name:	30mg alvelestat tablets	Placebo
Dosage Formulation:	Tablet	Tablet (identical in appearance to active)
Unit Dose Strength(s) / Dosage Level(s):	Days 1-5 (or 10): 240mg bid (8 x 30mg tablets bid)	Days 1-5 (or 10): 8 x tablets bid
Route of Administration	Oral	Oral
Dosing Instructions:	To be taken bid, 12 hours apart	
Packaging and Labeling:	Study treatment will be provided in wallets and will be labeled as required per U.S. regulations.	
Manufacturer:	Mereo BioPharma 4 Ltd., [name]	

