8.0 DISCONTINUATION CRITERIA

8.1 Discontinuation of Study Treatment

In considering discontinuation of the study treatment, the Investigator should give particular consideration of the following:

Liver Test Abnormalities

The following monitoring schedule is proposed when a case of acute liver function abnormalities or worsening of a liver function abnormality is reported:

- 1) If ALT or AST increases to $>3 \times$ ULN but $<5 \times$ ULN, in participants with normal transaminases at baseline, repeat testing within 48 to 72 hours including ALT, AST, ALP and Total Bilirubin [TB], should be performed and query for symptoms made. If repeat testing shows ALT or AST persists $>3 \times$ ULN (alternatively 2-fold increase above baseline for participants with abnormal values before study drug exposure), close observation is to be initiated as follows:
 - Regular monitoring (twice to three times a week) is required (AST, ALT, ALP and TB)
 - Initiate potential DILI evaluation for alternative etiologies. Testing for alternative etiologies can include serology tests (hepatitis A, hepatitis B, hepatitis C, Cytomegalovirus (CMV), Epstein-Barr Virus (EBV), Herpes Simplex Virus (HSV), varicella zoster virus (VZV), parvovirus, toxoplasmosis), imaging, and pathology assessments (creatinine phosphokinase, clotting) as appropriate to the clinical situation. Consider a hepatology consult.
 - Follow the patient, if laboratory parameters stabilize or normalize the patient can continue on study treatment during this period.

If the increase in ALT or AST to $> 3 \times$ ULN is also in association with abnormalities in TB or INR or with clinical hepatitis as specified below, study drug **MUST** be stopped.

- 2) If AST or ALT are $\geq 5 \times$ ULN, a repeat value should be obtained within 24-48 hours. If the repeat ALT OR AST values is $\geq 5 \times$ ULN, the drug should be discontinued and the patient followed until the laboratory values normalize or stabilize, in addition to initiating potential (Drug Induced Liver Injury) DILI evaluation.
- 3) When the following abnormal liver test conditions are met, study treatment **MUST** be discontinued, the study PI be informed, and further steps discussed:
 - ALT or AST $>3 \times$ ULN and total bilirubin $>2 \times$ ULN **OR**
 - ALT or AST $>3 \times$ ULN and international normalized ratio (INR) >1.5 **OR**

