- Absolute QTcF >500 ms or >60 ms increase from baseline as confirmed with 3 consecutive EKGs taken in a 30-minute period with at least 5 minutes between each EKG. The mean of the 3 EKGs will be used for decision making.

Acute Kidney Injury (AKI)

Alvelestat is predominantly renally excreted and the effect of acute kidney failure on PK is unknown. Participants who develop AKI requiring dialysis or hemofiltration must have study drug discontinued.

Other Laboratory Parameters

Study treatment **MUST** be discontinued if the following laboratory parameters criteria are met:

- Absolute neutrophil count less than or equal to $0.5 \times 10^9/L$ on 2 consecutive repeat tests within 48 to 72 hours.

Other

Study treatment **MUST** be discontinued if the following other criteria are met:

- Significant safety issues (as judged by the Investigator). This includes AEs considered unacceptable by the patient and/or the Investigator
- Any other protocol deviation that results in a significant risk to subject's safety
- Pregnancy as confirmed by positive urine test at any time during the study
- Withdrawal of informed consent.
- Progression to intubation/mechanical ventilation or other circumstance where continued administration of study drug tablets by the oral route is not possible.

Participants may voluntarily discontinue investigational treatment for any reason at any time. Participant decision on discontinuation of study treatment does not imply an automatic withdrawal from the study.

Refer to the Schedule of Assessments (SoA) for data to be collected at the time of treatment discontinuation (EoT) and follow-up and for any further evaluations that need to be completed.

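### In the 5-day course the first scheduled on-treatment safety blood falls on the last dosing day, so on scheduled bloods the two confirm-then-stop laboratory rules cannot prevent a dose

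*Protocol*

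**What the plan says.** Protocol Section 2.0 has a table headed "a) For subjects completing treatment at Day 5". Study drug is marked on Day 1, Day 2, Days 3 and 4, and Day 5. The row "Blood draw (screening and in-study safety monitoring" is marked at Screening, Day 1, Day 5 (EoT) and Day 10 only. The Day 1 sample is a baseline sample and can be left out: "If Screening and baseline are within 24 hours the tests do not need to be repeated at Baseline".

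Section 8.1 contains two laboratory stops that need confirmation:

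- **ALT or AST at or above 5 x ULN:** "a repeat value should be obtained within 24-48 hours", and drug is stopped if the repeat is still at that level.
- **ANC at or below 0.5 x 10^9/L:** the stop applies "on 2 consecutive repeat tests within 48 to 72 hours".

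Section 9.5.3 uses the same repeat requirement to define the neutropenia AESI. The synopsis and SAP Section 6.2 count AESIs to EoT.

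Section 5.8 says of hepatic risk that "close observation and frequent in-study monitoring, and study treatment discontinuation criteria are in place to protect the safety of the subjects". It says of neutropenia that "new onset of neutropenia will constitute a patient stopping criterion".

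**The concern.** A rule that waits for a repeat test can protect a patient only if the first abnormal value is found early enough for the repeat to come back while drug is still being given. In a 5-day patient the first on-treatment value that the schedule guarantees is taken on the last dosing day.

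Two things are at stake. First, the benefit-risk argument in Section 5.8 rests partly on monitoring and stopping rules that the schedule does not put in a position to work in this course. Second, safety and tolerability are the primary objective. If no 5-day patient stops for a confirmed laboratory value, or none has confirmed neutropenia by EoT, the schedule may be the reason, yet the result could be reported as good tolerability.

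**Working it through.** The plan gives no figure of its own on this point, so there is none to reproduce. The check is timeline arithmetic.

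**Inputs**

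- Dosing (Section 7.1): "To be taken bid, 12 hours apart", Days 1 to 5.
- First scheduled on-treatment safety blood (Section 2.0, table a): Day 5.
- Repeat windows (Section 8.1): 24-48 h for ALT/AST at or above 5 x ULN; 48-72 h for ANC.
- Assumption: first dose on the morning of Day 1 (hour 0) and the Day 5 sample that morning, at 4 x 24 = hour 96.

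**Doses.** At 12 h intervals from hour 0, there are 5 x 2 = 10 doses, the last at 9 x 12 = hour 108. Before the Day 5 sample, 4 x 2 = 8 of the 10 have been given.

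**Confirmation.** Confirmation time = draw time + repeat window. Doses avoided = doses due at or after confirmation.

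| Rule | Confirmed at | Study day | After last dose | Doses avoided |
|---|---|---|---|---|
| ALT/AST at or above 5 x ULN | 96 + 24 = 120 h to 96 + 48 = 144 h | 6-7 | 12-36 h | 0 of 10 |
| ANC at or below 0.5 x 10^9/L | 96 + 48 = 144 h to 96 + 72 = 168 h | 7-8 | 36-60 h | 0 of 10 |

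**Sensitivity to the assumptions**

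- With a first dose on the evening of Day 1 there are 9 doses, 7 of them before the Day 5 sample. The last is still at hour 108, and 0 of 9 are avoided under either rule.
- If the liver window is read only as an upper limit, a repeat on Day 5 before the evening dose could spare at most 1 dose.

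**What an earlier result would change.** Suppose a routine or unscheduled sample happened to be taken before the morning dose on another day. The doses still avoidable out of 10 would be as follows. This is an illustration, not a proposed schedule.

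| Day of first abnormal value | 24 h repeat | 48 h repeat | 72 h repeat |
|---|---|---|---|
| 2 | 6 | 4 | 2 |
| 3 | 4 | 2 | 0 |
| 4 | 2 | 0 | 0 |
| 5 | 0 | 0 | 0 |

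Whether these rules can act in a 5-day patient therefore depends on whether a result exists on Days 2 to 4.

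**Does anything require such a result?** Section 5.1 sends liver, renal and haematology tests after baseline to the schedule, and its list of items collected daily contains no laboratory test. The schedule's heading asks for a daily safety assessment but marks no blood on Days 2-4, although physical examination and SaO2/FiO2 are marked on those days. Table (b) marks the same blood row, with the same footnote 2, on Days 6-9, so the footnote is not used there in place of a mark. Footnote 2, Section 9.0 (unscheduled samples) and Section 9.4 (use of routine-care data) are all permissions.

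**AESI endpoint.** With EoT on Day 5 and ANC confirmation on Days 7-8, neutropenia first seen on the scheduled EoT sample cannot meet its AESI definition by EoT. Section 4.0 of the Protocol gives the cut-off as Day 14 or EoT. A Day 14 cut-off would include that confirmation, so the answer depends on which wording governs.

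**The case against.** A reader might infer that the hepatic and neutropenia risks have no working laboratory safeguard in the 5-day course. The documents do not support that, for four reasons.

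- **Routine results can be used.** Treated patients are inpatients, and those discharged early stop drug. Footnote 2 is attached to this very row, and Section 9.0 allows unscheduled safety samples. A Day 2-4 result could trigger and confirm a stop in time.
- **Not every stop needs confirmation.** Section 8.1 has liver criteria that stop drug at once (for example transaminases with raised bilirubin, raised INR or symptoms) and a stop on the investigator's judgement. Section 8.1.1 lets the investigator suspend dosing for an important laboratory abnormality.
- **Known abnormalities must be handled.** Section 9.4.4 and Appendix 2 require documented review of laboratory reports, and Section 9.4.4 requires clinically relevant changes to be recorded as adverse events. Section 9.5.3 makes any ALT/AST above 5 x ULN an AESI, whatever day it occurs.
- **The rules are not redundant.** They also serve patients who extend to Day 10, for whom a Day 5 finding still leaves dosing days and who have safety bloods marked on Days 6-9.

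Two other inferences also go too far. The rule for ALT/AST between 3 and 5 x ULN is not a stop rule, because a confirmed value leads to close observation. And the phrase about frequent monitoring in Section 5.8 concerns the liver only; for neutropenia that section cites exclusion, the stopping criterion and infections as an AESI.

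All of this stands, and it narrows the point without removing it. The routes to earlier action depend on a Day 2-4 result that nothing requires. On scheduled bloods, the immediate stops and investigator suspension can affect only the remaining Day 5 dose or doses. The recording duties apply to results that exist. Nor do the documents give a time course for liver or neutrophil effects, so it cannot be said that a peak on Days 2-4 would be missed, only that the schedule does not ensure it would be seen.

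**Conclusion.** The point holds for scheduled bloods. A 5-day patient has one scheduled on-treatment safety sample, on the last dosing day, and the two confirm-then-stop rules then spare 0 of 10 doses (0 of 9 with an evening start; at most 1 if a same-day liver repeat is accepted). Neutropenia first found on that sample cannot be confirmed as an AESI by EoT. This conflicts with the reliance placed on monitoring and stopping rules in Section 5.8, and the passages need to be reconciled.

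The result assumes 12-hourly dosing, a morning sample on Day 5 and the repeat windows as written. The practical size also depends on how often routine results are available on Days 2-4 and how many patients finish at Day 5; the documents give neither. The trial plans 15 patients, 10 of them on alvelestat, and Section 5.4 puts the mean hospital stay at 5 days, so the 5-day course is unlikely to be rare. The thresholds in Section 8.1 are not in question.

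**What to change.** 1. Reconcile Section 2.0 (table a), Section 5.8 and Section 8.1. Which schedule or stopping rule is right is for the sponsor to decide; none is proposed here.
2. Require that liver panel, creatinine and differential count results already obtained in routine care on Days 2-4 are entered in the CRF, reviewed against Section 8.1 and included in the safety-laboratory summaries. Section 10.3.1 summarises laboratory values by study visit, so state how results without a scheduled visit enter.
3. State whether an abnormality first seen on the Day 5/EoT sample and confirmed afterwards counts in the AESI endpoint, and align the cut-off between the synopsis, Section 4.0 and SAP Section 6.2.
4. If the sponsor does not take up these changes, correct the statement in Section 5.8. Say in the report that confirmed-value stops could not operate from scheduled bloods in 5-day patients, so their absence is not evidence of tolerability.

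The cost is wording and a little more data entry. Item 2 calls for no additional blood samples.
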